Official Title: Comprehensive Wide Bandwidth Test Battery of Auditory Function
in Veterans

NCT Number: 02019888

Document Date: 3/5/2021

Study Protocol

The goal of this research is to evaluate a comprehensive test battery of new wide-bandwidth, i.e., wideband (WB), acoustical tests of auditory function in the differential diagnosis of middle ear, cochlear and neural pathologies in a population of Veterans. WB tests refer to ear canal tests using sound responses measured from 200 Hz to frequencies as high as 8000 Hz, a bandwidth that is critical for speech perception. There will be tests in the battery for middle-ear assessment using absorbance cochlear assessment using otoacoustic emissions (OAEs) and the acoustic stapedius reflex (ASR) using middle ear power absorption. Results will be compared with a standard single-frequency clinical immittance test battery routinely used in the assessment of auditory function in Veterans.

Aim 1 seeks to evaluate the accuracy of the WB test battery in the differential diagnosis of middle-ear pathology and related conductive hearing loss by comparing the sensitivity and specificity of the WB battery to the traditional immittance battery for disorders common in Veterans including tympanic membrane perforation and serous otitis media. Aim 2 seeks to modify a WB ASR test to provide automatic detection of the ASR threshold for comparison with the traditional single-frequency ASR threshold. Aim 3 seeks to validate the use of Transient-evoked otoacoustic emission (TEOAE) and spontaneous otoacoustic emissions (SOAEs) tests in Veterans to assess cochlear status, and evaluate their test performance in classifying ears with normal hearing and sensorineural hearing loss. The combination of tests across aims will allow for examination of the diagnostic accuracy of the full WB test battery in comparison to the single-frequency admittance test battery to detect any type of hearing loss including sensorineural, conductive and mixed. The hypothesis is that the WB test battery is more accurate than the traditional immittance test battery in identifying ears with normal auditory status and ears with a range of risks for auditory pathology.

Methods:

Subjects- Human subjects will be recruited for this study who have had a hearing evaluation from the VA Audiology Service at the Portland VA Medical Center and the H. Quillen VA Medical Center. These subjects will respond to flyers or be contacted from an IRB-approved human subject volunteer registry. Data will be acquired from three groups of subjects with normal hearing, sensorineural hearing loss (SNHL), and middle ear disorders.

Testing- All subjects will receive the same clinical and WB test battery. Each subject will be tested in one laboratory visit. Subjects will be enrolled in this study that upon otoscopic inspection of their ear canals, have no active drainage from the ears, and have ear canals free of cerumen (wax) impaction, bilaterally. Subjects who are found to have draining ears or cerumen impaction will be referred for treatment. These individuals may be enrolled in the study following successful treatment for their conditions. All subjects will have a standard pure-tone air- and bone-conduction

audiogram while comfortably seated in a sound-treated booth. Standard insert earphones and a bone-conduction vibrator will be used to present the sound stimuli. Next, speech audiometry will be completed and the speech reception thresholds, uncomfortable loudness test for speech, and speech recognition scores will be obtained. Then the subjects will have a standard immittance test battery consisting of a tympanogram and acoustic reflex threshold testing. Stimuli will not exceed a level of 100 decibels hearing level (dB HL). Finally, the wideband test battery will be performed with adults seated comfortably in a sound-treated booth. A small probe with a soft rubber tip will be inserted in the subject's ear canal, and the subject will be asked to remain quiet while sounds are presented to an ear via sound sources within the probe. Responses will be measured using a miniature microphone within the probe. The tests in the wideband battery are similar to the clinical admittance battery and include ambient absorbance, absorbance tympanometry and acoustic reflex threshold. The otoacoustic emission testing is a separate measurement of inner ear function typically conducted in the clinic using different equipment.

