## **Statistical Analysis Plan**

Analyses of variance (ANOVA) will be conducted to examine differences in outcomes measures across the three subject groups with normal hearing (NH), sensorineural hearing loss (SNHL), and middle ear disorders (ME). Bonferroni corrections will be applied for multiple comparisons. T-tests will be used to examine effects of method (clinical vs. experimental wideband) within each subject group.

For the Primary Outcome measure of Middle Ear Test, separate ANOVAs will be used to examine differences across groups within each method. In the first ANOVA, the independent variable will be subject group, and the dependent variable will be clinical tympanometric peak static acoustic admittance at 226 Hz. In the second ANOVA, the independent variable will be subject group, and the dependent variable will be wideband absorbance at ambient pressure averaged across half-octaves from 250 to 8000 Hz.

For the Secondary Outcome measure of Middle Ear Muscle Reflex Test, separate t-tests will be used to examine the difference in middle ear muscle reflex threshold between the clinical and wideband experimental methods within each subject group.

For the Secondary Outcome measure of Wideband Otoacoustic Emission Test, an ANOVA will be used to examine the differences across subject groups in transient evoked otoacoustic emission (TEOAE) signal-to-noise ratio (SNR) (averaged across half-octave bands from 1000 to 8000 Hz).

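### Aim 1 promises a comparison of accuracy for conductive hearing loss, but the supplied SAP evaluates neither middle-ear test against any conductive-loss reference

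*Protocol*

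**What the plan says.** - **Target.** Aim 1 in the Protocol (Study Protocol, aims paragraph) concerns the "differential diagnosis of middle-ear pathology and related conductive hearing loss". The same paragraph later says the full battery will be examined for its accuracy "to detect any type of hearing loss including sensorineural, conductive and mixed".
- **Yardstick.** Aim 1 is to be judged by "comparing the sensitivity and specificity of the WB battery to the traditional immittance battery".
- **Data.** Under Methods, Testing, the Protocol states: "All subjects will have a standard pure-tone air- and bone-conduction" audiogram. The immittance and wideband tests are done at the same single visit.
- **Groups.** Under Methods, Subjects, data come from "three groups of subjects with normal hearing, sensorineural hearing loss (SNHL), and middle ear disorders". The supplied text gives no audiometric criterion for membership of any group.
- **Analysis.** For the primary outcome, the SAP says "separate ANOVAs will be used to examine differences across groups within each method". In the first of these, "the independent variable will be subject group, and the dependent variable will be clinical tympanometric peak static acoustic admittance at 226 Hz". The second has the same factor, with wideband absorbance at ambient pressure, averaged from 250 to 8000 Hz, as the dependent variable. The SAP also plans t-tests of clinical against wideband method within each group.

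**The concern.** Aim 1 has two targets: disease of the middle ear, and the conductive loss that goes with it. The SAP represents both by one three-level label. That label need not coincide with conductive loss. As far as the supplied text shows, the middle-ear group could pool ears with a large air-bone gap and ears with little or none.

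At stake is the conclusion the study wants to draw. Its hypothesis is that the wideband battery is the more accurate. If the SAP is followed exactly, the report can say whether mean admittance differs across groups and whether mean absorbance does. It cannot say how well either test detects conductive loss, or which does so better, although the audiogram needed for that question is planned for everyone.

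**Working it through.** **1. Promise against analysis.**

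| Element of Aim 1 | Protocol | Supplied SAP |
|---|---|---|
| Conductive loss as a target | Named in Aim 1 and again in the overall objective | Not used as an outcome, factor, covariate or reference |
| Data to define it | Air- and bone-conduction audiogram for all | Audiogram has no analytic role |
| Measure of performance | Sensitivity and specificity | Group means only |
| Comparison of methods | Wideband against traditional | Separate ANOVA per method; t-tests of method within group |

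**2. What the planned tests can show.** Each ANOVA tests whether the mean is equal in the normal-hearing, sensorineural and middle-ear groups, once for admittance and once for absorbance. Two separate p-values do not compare two methods. A within-group t-test of method compares average values, not the ability to separate ears with conductive loss from ears without it. No combination of these results yields a sensitivity, a specificity or a difference in either.

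**3. Plan figures to reproduce.** There are none: the supplied text states no sample size, alpha, standard deviation or effect size.

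**4. Could the group ANOVA stand in for a conductive-loss analysis?** This is an illustration on assumed inputs only:
- 30 ears per group; alpha 0.05; 4,000 simulated trials per setting.
- Gap near 0 (SD 4 dB) in the normal-hearing and sensorineural groups.
- In the middle-ear group, 20% or 40% of ears have no gap; in the rest the gap has mean 20 dB and SD 10 dB.
- Measure = −b × gap − s × (1 if middle-ear group) + error with SD 1.

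Percentage of trials with p < 0.05 (first figure for 20% of ears without a gap, second for 40%):

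| Setting | Three-group ANOVA | Regression on gap, all groups, no group term | Regression on gap, middle-ear group only |
|---|---|---|---|
| Measure follows the gap only (b = 0.03 SD per dB, s = 0) | 44, 27 | 84, 77 | 46, 51 |
| Disorder shifts the measure, no relation to the gap (b = 0, s = 0.8 SD) | about 89 in both | 67, 51 | about 5 |

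With both effects present (b = 0.015, s = 0.5), the ANOVA rejects in 82% and 76% and the pooled regression in 85% and 72%.

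Three things follow.
- In the second setting the ANOVA is significant in about 89% of trials although the measure is unrelated to the gap within the middle-ear group. A significant ANOVA is thus no evidence about conductive loss as such.
- Which test has more power depends wholly on the assumed model: regression is ahead in the first setting, the ANOVA in the second.
- A regression pooled over all groups without a group term rejects in 51% to 67% of trials when the gap has no effect within the middle-ear group, because it picks up the group difference again. The within-group regression rejects at about the nominal 5%.

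**The case against.** **The ANOVAs may already bear on conductive loss.** If entry to the middle-ear group required an air-bone gap, the group contrast would be partly a conductive-loss contrast. The group criteria are not in the supplied text, so this cannot be excluded, and it would be too strong to say that conductive loss is wholly untested. Even then, neither ANOVA gives accuracy or compares the methods.

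**Part of the SAP was removed before review.** The absence can be stated only for the supplied text. That limit stands.

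**Aim 1 asks for accuracy, not correlation with a graded gap.** This stands, and it shapes the remedy. The supplied SAP has no sensitivity, specificity or ROC comparison for any target; the conductive-loss gap is one part of that broader omission. The air-bone gap is not named in the documents. Using it as the reference is this review's proposal, made because the planned audiogram is the only direct source of a conductive-loss measure that they describe.

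**A stronger reading: power is lost.** A reader might infer that reducing a graded gap to a group label costs the trial power. The documents do not support this. They give no inputs from which power could be computed, and leaving out an analysis does not lower the ANOVAs' power for their own hypothesis, that group means differ. The simulation favours regression only when the measure is assumed to follow the gap, and the order reverses under the other assumption.

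**Conclusion.** The point holds as a mismatch between aim and analysis. Conductive hearing loss is a named target of Aim 1, the data to define it are planned for every subject, and no analysis in the supplied SAP evaluates 226-Hz admittance or wideband absorbance against it or compares their accuracy. This rests on the wording of the two documents and on no numerical assumption.

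Its size is one named part of Aim 1 without a matching analysis; no power figure can be attached to it. The planned ANOVAs remain valid for the question of group means. The change is worth making before analysis because it is cheap and because, without it, the comparison of the two methods for conductive loss stays unanswered. The finding would be narrowed if the removed SAP text, or group criteria not supplied, already contained such an analysis or reference.

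**What to change.** Keep the two group ANOVAs and add one prespecified secondary analysis for Aim 1.

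1. **Reference.** Define conductive loss per ear from the study-visit air-bone gap. Fix the frequencies and cut-off in the SAP before analysis, with a range of cut-offs as a sensitivity analysis. State how mixed losses and thresholds beyond the equipment's output are handled, and whether one or both ears enter.
2. **Accuracy.** For 226-Hz admittance and for mean wideband absorbance, estimate the ROC area and the sensitivity at one fixed specificity against that reference.
3. **Comparison.** Report the paired difference between methods in each quantity, with a confidence interval from a bootstrap that resamples subjects, so that two ears from one person stay together.
4. **Support.** Report the association of each measure with the graded gap within the middle-ear group, or with a group term in the model, so that it is not merely the group contrast in another form. The overall ROC area also draws partly on easy contrasts with normal-hearing ears, so the two results should be read together.

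The cost is SAP text and one further analysis on data already planned. The downside is one more secondary comparison, whose place in the Bonferroni scheme should be stated.

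### No age range, matching or age adjustment is stated for the three hearing-status groups, so an age difference between them could be read as a pathology effect in the between-group ANOVAs

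*Protocol*

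**What the plan says.** **Recruitment (Protocol, Methods, Subjects).** "Human subjects will be recruited for this study who have had a hearing evaluation from the VA Audiology Service" at two VA centres. "These subjects will respond to flyers or be contacted from an IRB-approved human subject volunteer registry". Groups follow hearing status: "Data will be acquired from three groups of subjects with normal hearing, sensorineural hearing loss (SNHL), and middle ear disorders".

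**Enrolment conditions (Protocol, Methods, Testing).** The stated conditions are otoscopic. Subjects must "have no active drainage from the ears, and have ear canals free of cerumen (wax) impaction, bilaterally". The one wording that touches age describes the procedure: "the wideband test battery will be performed with adults seated comfortably in a sound-treated booth". That implies a lower bound and nothing more.

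**Between-group analysis (SAP, Statistical Analysis Plan).** The general statement is "Analyses of variance (ANOVA) will be conducted to examine differences in outcomes measures across the three subject groups". For the primary middle-ear outcome there are two ANOVAs, one on 226 Hz peak admittance and one on wideband absorbance. Both name the same single independent variable, as here: "In the second ANOVA, the independent variable will be subject group". For the emission outcome, "an ANOVA will be used to examine the differences across subject groups in transient evoked otoacoustic emission (TEOAE) signal-to-noise ratio". No covariate, age stratum or sensitivity analysis is named.

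**Within-group analysis (same section).** Clinical and wideband methods are compared by t-tests inside each group, including for the reflex threshold.

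**The concern.** The groups are not randomised, so nothing in the design balances age across them. They are defined by hearing status, and acquired sensorineural loss is generally more common at older ages. An NH group younger than the SNHL group is therefore plausible, although the documents give no ages.

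The aims in the protocol's opening section depend on attributing differences to middle-ear or cochlear status. With group as the only factor, any age trend in admittance, absorbance or TEOAE signal-to-noise ratio is absorbed into the group term. It matters most where little pathology difference is expected, namely NH versus SNHL on the two middle-ear measures. There, an age effect could be mistaken for a finding about the ear. For TEOAE a real difference is expected, and the risk is that part of its size is due to age.

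**Working it through.** **No figure to reproduce.** The documents state no sample size, standard deviation, effect size, alpha or age. The arithmetic below rests entirely on assumptions.

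**Assumed inputs**
- No true pathology effect; two-sided alpha 0.05.
- Outcome scaled to a within-group SD of 1.
- r = within-group correlation of age with outcome, the same in each group.
- g = NH-SNHL gap in mean age divided by the within-group age SD. With SD 10 years, a 10-year gap is g = 1 and a 20-year gap is g = 2.
- ME mean age midway between NH and SNHL.
- n = 30 per group, then larger.

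**Step 1: spurious difference.** NH versus SNHL is shifted by d = r × g SDs. For r = 0.1, g = 1, d = 0.10. For r = 0.3, g = 2, d = 0.60.

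**Step 2: effect on the three-group test.** The group means are 0, d/2 and d. Their squared deviations from the overall mean sum to d²/2, so the noncentrality parameter is λ = n × d²/2. The F statistic has 2 and 3n − 3 degrees of freedom. At n = 30 that is 2 and 87, with a 5% critical value of 3.10.

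| r | Age gap (years) | d | λ (n = 30) | False rejection |
|---|---|---|---|---|
| 0.1 | 10 | 0.10 | 0.15 | 6.1% |
| 0.2 | 5 | 0.10 | 0.15 | 6.1% |
| 0.2 | 10 | 0.20 | 0.60 | 9.6% |
| 0.3 | 10 | 0.30 | 1.35 | 16.0% |
| 0.2 | 20 | 0.40 | 2.40 | 25.6% |
| 0.3 | 20 | 0.60 | 5.40 | 52.2% |

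**Step 3: sample size.** λ grows in proportion to n. At r = 0.3 and a 10-year gap (d = 0.30), λ is 1.35, 2.70 and 4.50 for n = 30, 60 and 100, and false rejection is 16%, 29% and 46%. Simulation of the same settings (3,000 runs each) gave 15%, 28% and 44%.

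**Step 4: Bonferroni.** For the NH-SNHL pair at 0.05/3, the rejection probability is approximately Φ(d√(n/2) − 2.394). With d = 0.30 and n = 30 this is Φ(1.162 − 2.394) = Φ(−1.232) = 11%. It is 23% at n = 60 and 39% at n = 100, against a nominal 1.7%. A stricter threshold does not remove a bias.

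**Step 5: with age in the model.** In simulations with r from 0.2 to 0.4, gaps from 0 to 1.5 SDs, and n of 30, 60 or 100, adding age as a linear covariate held false rejection between 4.1% and 5.8%. This is expected, because the data were generated with the same linear, common age slope that the model fits.

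**Step 6: which analyses are touched.** The two primary ANOVAs and the TEOAE ANOVA compare groups and are exposed. The t-tests compare two methods inside one group, so a difference in age between groups does not bias them.

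**The case against.** - **The documents are silent; they do not say that age was unrestricted.** A reader might infer that recruitment had no age limit. The text does not support that: the protocol is a short summary, and it does refer to adults. What stands is that no age range, matching or adjustment is stated.
- **The inputs come from outside the documents.** No age gap and no relation between age and outcome is given. With r = 0.1 and a 10-year gap the inflation is about one percentage point, and with a weaker relation it would be smaller still. This stands, so the result must be shown as a range that begins near nominal.
- **The no-effect null is unrealistic for much of the plan.** Real differences are expected for TEOAE in SNHL and for the middle-ear measures in ME. This stands: a false-positive rate speaks mainly to NH versus SNHL admittance and absorbance. The shift d is still added to or subtracted from a real difference under the same assumptions, so the TEOAE estimate is not exempt.
- **Every subject receives both batteries.** A reader might infer that the clinical-versus-wideband comparison is itself biased by age. The within-group t-tests are not, and age composition is common to both methods.
- **Adjustment is not free of harm.** Age may be part of the cause of SNHL, so a covariate can remove real signal, and it extrapolates where group ages barely overlap. This stands, and is why the adjusted model should sit beside the planned one and not replace it.

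**Conclusion.** The concern holds in a limited form. As written, the plan would attribute any age trend to subject group in the admittance, absorbance and TEOAE ANOVAs. The exposure is greatest for NH versus SNHL on the two middle-ear measures and partial for TEOAE.

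The size cannot be known from the documents. Under the stated assumptions with 30 per group, it runs from negligible (about 6% against a nominal 5%) to serious (about 52%), and more subjects make it worse.

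A reader might go further and conclude that the groups are in fact imbalanced on age, or that an observed group difference would be an artefact. The documents contain no age data and support neither. Nor do they make age-matched quotas necessary: quotas slow the recruitment of older NH subjects, and their value here is debatable. The conclusion rests on the SAP text available for review.

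**What to change.** In the SAP's Statistical Analysis Plan section:

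1. Keep the planned unadjusted ANOVAs.
2. For admittance, absorbance and TEOAE signal-to-noise ratio, add the same model with age as a covariate and report both results side by side.
3. Report the age distribution (mean, SD, range) in each group.
4. State that where group ages barely overlap, the comparison will be restricted to the overlapping age range.
5. State the limitation that adjustment may remove part of a real SNHL effect.

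The cost is a few sentences, one table and one residual degree of freedom per model (87 to 86 with 30 per group). Age must be recorded for each subject, which the documents do not mention. Restriction to the overlap loses subjects and precision. Balancing age when calling from the volunteer registry is optional; it would strengthen the comparison but slow enrolment of older NH subjects.

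### Reflex threshold is measured clinical first, wideband second in every subject, so the Aim 2 method t-tests estimate method plus order

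*Protocol*

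**What the plan says.** Under Methods, Testing, the Protocol states that "All subjects will receive the same clinical and WB test battery" and that "Each subject will be tested in one laboratory visit". It then sets out a sequence: audiogram, speech audiometry, clinical immittance, wideband. Of the third step it says "Then the subjects will have a standard immittance test battery consisting of a tympanogram and acoustic reflex threshold testing"; of the last, "Finally, the wideband test battery will be performed with adults seated comfortably in a sound-treated booth". The wideband tests "include ambient absorbance, absorbance tympanometry and acoustic reflex threshold", so each subject has two reflex thresholds, the clinical one first. Neither document mentions randomised or counterbalanced order, a rest interval or repeat testing.

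Taking the three groups one at a time, the SAP says of this secondary outcome that "separate t-tests will be used to examine the difference in middle ear muscle reflex threshold between the clinical and wideband experimental methods". Its opening paragraph describes the purpose of such tests: "T-tests will be used to examine effects of method (clinical vs. experimental wideband) within each subject group". No order or period term appears, and the SAP does not say whether the t-tests are paired. Aim 2 in the Protocol makes the comparison of wideband with traditional reflex threshold a study aim.

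**The concern.** The SAP interprets the clinical-versus-wideband difference as an effect of method. But method and position in the session are perfectly aligned: clinical is always earlier, wideband always later. If reflex threshold moves between the first and second measurement for any reason, that movement counts as method. It could create a difference between methods that agree, or hide one between methods that differ, so a reported agreement is as exposed as a reported difference. Since Aim 2 rests on this comparison, neither result could be attributed to method alone.

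The reach is limited. The two primary ANOVAs and the TEOAE ANOVA compare groups that share one order, so an order effect common to the groups does not bias them. No effect on the Aim 1 accuracy comparison is claimed.

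**Working it through.** **What the contrast estimates.** Let m be the true wideband-minus-clinical difference and o the mean change in reflex threshold from first to second test. With clinical first in everyone,

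E[wideband − clinical] = m + o.

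There is one equation and two unknowns, and a larger n only estimates the sum more precisely. This holds for a paired or an unpaired t-test, because both use the same mean difference.

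**Inputs.** The documents give no sample size, SD, alpha or expected difference, so there is no figure of the plan's to reproduce. Everything below is assumed, for illustration:
- m = 0; two-sided alpha 0.05; paired t-test.
- SD of paired differences s = 5.66 dB, from 4 dB per method (4 × √2), with 4 and 8 dB as a range.
- n = 20, 30 or 50 per group; o = 0, 0.5 or 1 dB.

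**Formula.** The rejection probability is P(|T| > t(0.975, n−1)), where T is noncentral t with n−1 degrees of freedom and noncentrality (o/s)√n. Example: o = 1, s = 5.66, n = 30 gives (1/5.66) × √30 = 0.968, critical value 2.045, rejection probability 15.5%.

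| Chance of a significant method difference when m = 0 | n = 20 | n = 30 | n = 50 |
|---|---|---|---|
| No shift | 5% | 5% | 5% |
| 0.5 dB, s = 5.66 | 6.6% | 7.5% | 9.4% |
| 1 dB, s = 5.66 | 11.7% | 15.5% | 23.2% |
| Shift that doubles the rate to 10%, s = 5.66 | 0.87 dB | 0.70 dB | 0.53 dB |

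At n = 30, s = 4 gives 10.2% (0.5 dB) and 26.3% (1 dB); s = 8 gives 6.3% and 10.2%.

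**Bonferroni.** The SAP says "Bonferroni corrections will be applied for multiple comparisons" without naming the family. If it covered the three groups (alpha 0.05/3 = 1.7% per test), the rates at s = 5.66 would be 2.4/2.9/3.8% for 0.5 dB and 4.9/7.1/11.9% for 1 dB. The correction lowers the rates but does not touch the bias.

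**Unpaired reading.** If an unpaired test were applied to these same-subject data, with 4 dB within-method and 4 dB between-subject SD (200,000 simulated trials), the rates for n = 20/30/50 would be 0.7/0.7/0.6% with no shift, 1.2/1.3/1.7% at 0.5 dB and 2.7/3.7/6.5% at 1 dB. The test becomes insensitive, but the estimated difference is still off by the full shift.

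**With randomised order.** Clinical-first subjects estimate m + o₁ and wideband-first subjects m − o₂. The average of the two sequence means is m + (o₁ − o₂)/2. When the shift is the same in both sequences, it cancels: simulated rejection (100,000 trials, n−2 degrees of freedom) is 5.0–5.1% for shifts of 0.5 and 1 dB. If o₁ and o₂ differ by 1 dB, 0.5 dB of bias remains and rejection is 6.6–9.4%.

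**The case against.** The strongest reply is that the harm is hypothetical. Nothing in the documents indicates that reflex threshold drifts within a visit. The measurement is passive, and wideband detection is to be automatic, which leaves little room for practice effects or for the examiner to influence the second test. The rates rest wholly on assumed inputs: at s = 5.66 a 0.25 dB shift gives only 5.4/5.6/6.1%. Under the unpaired reading with 4 dB between-subject SD, five of the six shifted cells stay below 5%. An exact-zero method difference is also a convenient null, because the two methods measure different things and the documents never hypothesise equal thresholds. Finally, the order is read from a short narrative, and separating the clinical reflex test from its battery alters the routine comparator.

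Much of this stands, and it limits the weight of the point. The size is unknown and the rates show sensitivity, not expected error. Counterbalancing might be specified in an operating manual; if so, one Protocol sentence settles the matter. What does not fall is the identification argument: it needs no assumed shift, SD or null, and the bias is the same if the methods truly differ. A passive test may still respond to earlier sound presentation, to tympanometry or to restlessness, and the design gives no means of showing that it does not. If clinical-first is kept because it is routine, the result is a difference under clinical-first testing and should be described that way.

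**Conclusion.** The concern holds as a minor point. As written, the within-group t-tests of reflex threshold estimate method plus order, and nothing in the Protocol or SAP separates the two. The bias equals the shift between first and second test, decibel for decibel; it is zero if there is no shift. The conclusion rests only on the fixed sequence in the Protocol and the absence of an order term in the SAP. The false-significance figures rest additionally on assumed pairing, SD, group size and shift. Confidence is medium because the order comes from a summary description of the visit.

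**What to change.** **If testing is still open.** Randomise the order of the two reflex-threshold tests only, 1:1 and blocked within each group. Keep the other tests in their present sequence as far as the equipment allows, for example by placing both reflex tests after the other measures, so that admittance, absorbance and TEOAE keep one position for everyone. State in the SAP that reflex threshold is analysed within each group by a paired method contrast adjusted for sequence, and report the difference with its confidence interval. State also that this removes the order effect only if carryover is equal in the two sequences.

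**Cost.** A randomisation list, one Protocol sentence and a sequence term in three analyses. The 95% half-width is t(0.975, df) × 5.66/√n, with df falling from n−1 to n−2: 2.65 to 2.66 dB at n = 20, 2.11 to 2.12 dB at n = 30, and 1.61 dB either way at n = 50. The workflow becomes slightly more complex, with possibly one or two extra probe changes per ear if the methods use different instruments, which the documents do not say.

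**If only whole batteries can be swapped.** Order terms are then needed in six models (three reflex, two primary, one TEOAE), and the primary measures are taken in mixed positions.

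**If testing is complete.** Add one reporting sentence: the reflex-threshold difference combines method and order and is not attributed to method alone.
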